- b. The use of personal mobile phones for the improvement of ART adherence among adolescents living with HIV is feasible and acceptable.
- c. ART adherence among adolescents is predicted by demographic, socioeconomic, and psychosocial factors.

METHODOLOGY

The proposed study is targeted at adolescents living with HIV/AIDS who are on ART but are not adherent to medications. Two hundred participants will be recruited to participate in a randomized controlled trial to evaluate the effectiveness of interactively tailored SMS reminders on the improvement of ART adherence. The study will be conducted in Ogun State in the southwestern part of Nigeria over a 52-week period.

Participants and setting

Nigeria has 36 states in six geo-political zones. The Southwest geopolitical zone is one of the six and consist of six states namely, Ogun, Lagos, Oyo, Osun, Ondo and Ekiti states. The study will be based in Ogun State and extend to the other five states in Southwest Nigeria in order to meet recruitment goals. Ogun State is one of the 36 states in Nigeria. Ogun State has an estimated 161,200 PLHIV living with HIV and an HIV prevalence rate of 3.1%. Thirteen thousand five hundred (13,500) PLHIV are currently accessing antiretroviral drugs across 24 treatment clinics in the State.

Study design and procedure

A single-blind, parallel-design (ratio 1:1), and multi-center RCT of 200 adolescent living with HIV who are non-adherent to medications will be conducted over a one-year period at HIV clinics in Ogun State and other states in Southwest Nigeria. This study is designed to have 80% power to detect a difference of 20%. When the proportion of adolescents who are adherent to ART was taken as 49% (6) and 10% attrition rate, a sample size of 96 per group was obtained using STATA 15/C statistical software. The study will recruit 200 participants from the ART clinics in Southwest Nigeria into a randomized controlled trial (RCT). Convenience sampling method by which participants will be recruited on routine clinic visits across five (5) high patient-density ART sites will be used.

Participants' recruitment

Recruitment of participants will occur over a three-month period. Recruitment will be based on five eligibility criteria namely:

- a. HIV seropositivity
- b. Being on ART for at least six months
- c. Age 15 to 19 years as at last birthday
- d. Use of personal mobile phone
- e. Poor adherence to ART

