All the participants will be enrolled into a "whatsapp" group where they will discuss satisfaction with ART services provided to them. An expert will be involved on the group to offer counsel on issues of client satisfaction with ART services. All the participants will also receive a simple clinic-based intervention that is based on stress and coping theories and cognitive behavioural therapy which is aimed at improving their mental status.

Follow-up

The follow-up visits will hold every four weeks at 4, 8, 12, 16, and 20 weeks after the baseline to coincide with the participants' routine clinic visits. ART adherence and client satisfaction will be assessed at each follow-up visit. The participants will also receive the adherence counseling by trained counselors at each visit. CHIV viral load assessments will be done at Baseline and 20 weeks. In order to complete the study, a participant is required to attend all follow-up visits.

[figure not shown]

Figure 1: Randomized controlled study design

Adherence counseling

In this trial, the counselors will be female master's degree level social workers with ART counseling experience. The adherence counselor will be mentored and will be supervised by the investigators. Adherence counseling will be conducted in a setting that mimics a typical ART clinic setting. Each session will consist of a 15 minutes face to face session and will deliver information on the impact of HIV on the

human immune system, the role of ART, the importance of adherence, the characteristics and consequences of non-adherence, and strategies to enhance adherence. The '5As of adherence' approach will be used (38).

Trial Assistance

The trial assistants will be bachelor's degree holders in relevant disciplines and with relevant research experience. They will be trained in research ethics, the study protocol, data collection tools, and data entry. They will obtain a signed informed consent from participants and allocate unique identifiers to them. The trial assistants will also administer the questionnaires, enter data into analysis software and assist participants in getting laboratory investigations done.

Trial Coordination

This trial will be coordinated on a day-to-day basis by a coordinator who will be an MPH degree holder with relevant experience in research coordination.

EXPECTED OUTCOMES

Primary outcome measure (ART adherence)

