Ethical consideration

Ethical approvals will be obtained from the Babcock University Human Research Ethics Committee (BUHREC) and Ogun State Ministry of Health Ethics Board. All the necessary permissions will also be obtained. A signed consent will be obtained from all participants. Participation will be entirely on voluntary basis and participants will be free to withdraw participation from the trial at any time without any negative consequence. Confidentiality of data and samples will be maintained. Data collection will be carried out in private rooms. Mobile phone numbers and all other participant details will be used for the purpose of the research only. Hard and soft copies of collected data will be stored in secure cabinets and password-secured laptops respectively. Only the data and PI will have access to the data. After the project, only the PI will have access to the data while the soft data will be encrypted and saved on an external drive and in the cloud. Physical data will be retained for 5 years while soft data will be retained for 10 years.

All the study participants will receive ART adherence counseling at each visit. They will also receive 5000 Naira at each visit to compensate for the cost of transportation, time and other additional costs of SMS, feedback phone calls and data.

All the study staff and investigators will be required to complete and pass the Nigerian National Code for Health Research Ethics online.

Data and Safety Monitoring Plan

The intervention is not associated with any defined significant adverse effect. Data and safety monitoring will be overseen by the principal investigator. He will ensure that participants' rights are protected. The

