trial coordinator will make sure ensure that all required documentation and reports are timely, complete, and accurate. The counselors will ask study participants for symptoms of adverse reactions and side effects of ART at every contact. The data manager will routinely assess the collected data for accuracy and completeness. She/he will also make sure that data collection aligns with study the protocol and keep data-collection tools in a secured locker and restrict access to data. Bi-monthly review meetings will be held to ensure that the project proceeds as planned. A data use agreement will be signed with the medical internet technology solutions firm for the protection of participants' data and privacy. All participants' data will be held in sacred trust and exchanged only with the project and will not be used for any other purpose whatsoever.

Data Analysis

The research assistants will code and enter the data obtained into Microsoft excel software in the CSV format. The data will be exported to the STATA C version 15 for analyses. The data manager will fully review 5% (one in every twenty) questionnaire for errors. The data manager in conjunction with the investigators will be responsible for baseline, interim and final data analysis. The investigators, data manager, research assistants, counselors and other project staff will be blinded throughout the study. An independent medical internet technology firm will be contracted to randomize participants and to send the required SMS to the participants. After the scientific review has been completed and data collection has been completed, at the point of analysis, a list of participants' unique identifiers in two groups will be sent to the data analysts without specifying which the investigation or control group is. The blinding of the clinical database will finally be removed after final data analysis has been completed.

Statistical Methods

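### The all-participant WhatsApp group shows each identifiable member's HIV status to the others, and the protocol describes no identity protection and no way to decline the chat while staying in the trial

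*Combined protocol and SAP*

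**What the plan says.** The Intervention section enrols participants of both arms in a WhatsApp "group where they will discuss satisfaction with ART services provided to them". It adds one other person: "An expert will be involved on the group to offer counsel on issues of client satisfaction with ART services". That role concerns satisfaction with services; no privacy role is described.

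The entry criteria under Participants' recruitment include "HIV seropositivity", "Being on ART for at least six months" and use of a personal mobile phone.

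The statements on privacy are these:

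- Ethical consideration: "Confidentiality of data and samples will be maintained", and "Mobile phone numbers and all other participant details will be used for the purpose of the research only".
- Data and Safety Monitoring Plan: after a sentence on the data use agreement with the SMS firm, all participants' data are to be "exchanged only with the project and will not be used for any other purpose whatsoever".
- Baseline activities: consent and baseline data collection take place in a private room, and the SMS texts are to be worded so as to protect privacy.

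Nothing comparable to the last item is said about the chat.

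**The concern.** The plan takes care over privacy elsewhere, with private rooms, discreet SMS wording and restricted access to data. It then adds a component for everyone whose membership list is by construction a list of adolescents living with HIV. Its declared subject is their HIV treatment service, so membership is enough to disclose and no one needs to write anything.

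The plan itself recognises what is at stake. Its text on mental health status, under Secondary outcome measures, says that stigma, discrimination and social isolation worsen the mental health of adolescents with HIV and may lead to poor adherence. Members share the diagnosis, but nothing described in the protocol binds them to keep each other's status private, so it could be passed on.

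This is a different issue from contamination between arms. Separate groups for each arm would deal with contamination but would still show each member's status to the rest of that arm.

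**Working it through.** The plan states no figure on this point, and it does not depend on alpha, power, effect size or attrition. The check consists of reading the sections side by side, plus one count.

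**Step 1: who is in the group.** Intervention: all participants, both arms, plus one expert.

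**Step 2: what membership implies.** Participants' recruitment: HIV infection and at least six months on ART are conditions of entry. So 100% of participant members are HIV positive and on ART, and anyone who knows what the group is knows this of every member.

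**Step 3: who can see it.** Study design and procedure plans 200 participants. In the single group that the text describes, each member faces

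200 − 1 = 199 other participants.

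With 1:1 allocation and one group per arm, each would face about

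200/2 − 1 = 99 others.

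Both are upper limits. They assume that everyone joins and that members can be identified by name or number. The documents do not say whether names or numbers are visible. Identifiability is a reasonable assumption for a chat on personal phones with no masking described, but it remains an assumption.

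**Step 4: comparison with each privacy statement.**

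| Statement | Fit with the group chat |
|---|---|
| Data and Safety Monitoring Plan: data exchanged only with the project | Clearest tension, since other participants are not the project. The sentence follows the SMS firm's agreement but is worded for all participants' data. |
| Ethical consideration: confidentiality of data and samples | Tension with the general promise, although the surrounding sentences are mainly about collected data, storage and access. |
| Ethical consideration: phone numbers used for research only | No breach, because the chat is a study procedure. |
| Baseline activities: SMS worded to protect privacy | Covers the SMS only and leaves the chat without an equivalent. |

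**Step 5: safeguards for the chat.** The available text describes no pseudonyms, number masking, ground rules or privacy moderation. It describes no option to decline the chat and stay in the trial.

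**The case against.** The strongest reply is that this is an omission, not a conflict. The confidentiality sentences deal with collected data and with the SMS firm, and what participants learn of each other in a group is arguably outside them. Participation is voluntary and withdrawal is free. The consent pages are not in the available text and may already describe the chat or make it optional. The others in the chat share the diagnosis, and some may already meet at clinic.

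Part of this stands. A reader might infer that the plan flatly contradicts its own rules. The documents do not support that: the research-only clause is not breached, and the sentence in the Data and Safety Monitoring Plan can be read as a limit on the firm. A reader might also infer that the chat is compulsory. The protocol does not say so. The freedom to withdraw applies to the trial as a whole, and the Follow-up section ties completion to attending visits, not to the chat. What the consent form says cannot be judged here.

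The rest does not remove the point. Carried out as written, the procedure shows the status of any identifiable member to the others, which is more than a missing detail. Consent wording would make the disclosure known but would not by itself reconcile the sections. Meeting at a clinic is not the same as a shared list that, under the planned five recruiting sites, could cover participants from all of them.

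**Conclusion.** The point holds as a gap in participant protection and as sections that need reconciling. Its size is disclosure to up to 199 other participants per person, assuming one group, all 200 enrolled, and visible names or numbers.

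Two stronger readings should be resisted:

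- Someone might multiply out to 200 × 199 = 39,800 disclosures. That counts ordered pairs under the same assumptions, and further assumes that no member's status is already known to another. It is an upper bound and not an estimate of risk.
- Someone might argue that the chat will drive withdrawal or distress and so distort the completion-based feasibility measure or the GHQ-12. Nothing in the documents shows this, leaving the chat would not in itself make a participant a non-completer, and both arms are enrolled alike. No effect on between-arm results is claimed, and sample size and power are untouched.

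The change is worth making because it is inexpensive and the group is one that the plan itself describes as vulnerable to stigma.

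**What to change.** Amend the Intervention section so that:

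1. joining the group is voluntary and separate from trial participation, so that declining or leaving has no bearing on it;
2. participants are told before they join that other members will learn their status, and the consent wording is checked to confirm that it says so;
3. members' names and numbers are not visible to one another, through pseudonyms or masked numbers;
4. those who decline can receive individually delivered messages and one-to-one contact with the expert.

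Then bring Ethical consideration and Data and Safety Monitoring Plan into line, so that the text on confidentiality and on who receives participants' data covers the chat.

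Replacing the group altogether with one-to-one messaging would also close the gap, but it is a debatable trade. It removes a peer component whose subject, satisfaction with services, is a secondary outcome, and it could leave the expert with up to 200 separate conversations. The documents do not require going that far.

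The cost is protocol and consent wording, less peer discussion where members decline or are masked, and some repeated work for the expert. Sample size, randomization and outcomes do not change.

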ART adherence will be assessed using the visual analog scale (VAS), Viral load, Pill count, Pharmacy record, and the AIDS Clinical Trials Group (ACTG) adherence questionnaires at baseline and during every follow-up visits. The VAS has been found to be reliable, valid and suited for patients in resource-limited settings with insufficient human resources for time-consuming adherence assessments. It showed the highest sensitivity to detect patients with possible virologic failure at 95% cut-off for non-adherence (1, 39).

Secondary outcome measures

1. Patient satisfaction

Patient satisfaction is a potent predictor of ART adherence (40, 41).

2. Mental health status

Mental illnesses are varied, especially among adolescents because they experience a range of emotional, social and physical changes. The effects of mental illnesses on adolescents vary and can be acute, chronic, mild or severe. The commonest mental illnesses among adolescents are depression and anxiety disorders. Adolescents living with HIV have additional risk factors that increase their susceptibility to mental illnesses. This increased vulnerability may result from the loss of family, having to live independently, with relatives or in care. They are often exposed to poverty and violence. The stigma, discrimination, and social isolation that is associated with HIV further impact mental health negatively. They may result in poor adherence to ART (8).

The General Health Questionnaire (GHQ) 12 will be used to assess the mental health status in this study. The GHQ which was developed in 1970 by Goldberg to measure the current mental health has since been used in different settings and different cultures (42). The questionnaire was originally developed as a 60-item instrument but many shorter versions have been developed over time. The GHQ-12 is brief, simple, easy to complete, and has been widely used in research settings as a screening tool. It is a consistent and reliable instrument when used in the general population (42, 43).

Process measures

An ART adherence checklist will be completed by the counselors during each counseling session. The filled checklists will be examined to monitor the adequacy of counseling sessions. The participants will be required to send a reply SMS as soon as possible after ART and follow-up reminders are received. This will help confirm that SMS are delivered to participants and serve as a measure of feasibility and acceptability of the intervention.

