ART adherence will be measured at baseline and at every follow-up visit. Complete case analysis and the intention-to-treat analysis will be carried out. Baseline characteristics will be compared using the chi-square test, rank-sum test, and independent t-test as appropriate. The proportion of participants who are adherent to ART [$\geq 95\%$] at the end of the follow-up period will be compared with the baseline data using the chi-square test. The independent t-test will be used to compare the means of ART adherence between the investigation and control groups after each follow-up visit in order to test if the intervention has any effect. The incidence proportion, incidence rate, relative risk, risk difference, and odds ratio will be used to measure the effect. Multiple regression analyses will be used to control for possible confounders. Subgroup analysis will also be undertaken in order to generate further hypotheses. Survival analysis will also be carried out to adjust for

censoring (competing risk and loss to follow-up). Longitudinal data analysis will be carried out to explore the change in response over time.

The acceptability of the SMS will be accessed by the responses given by participants. The proportion of participants who find the method acceptable will be determined.

The feasibility will be determined using the proportion of participants who are deemed to have completed the study (participate fully).

The study will also assess client satisfaction and the possible effect of adherence on mental health status of adolescents. Correlation and linear regression analyses will be used to determine the association between adherence (percent) and mental health status (GHQ 12 measure).

PROJECT ACTIVITIES AND IMPLEMENTATION

Figure 1 shows a synopsis of the intended activities, RCT design the overall flow during the study.

Timeline

Activity	Period (week)
Initial Planning, Procurement, recruitment and training of project staff	1 to 13
Review meetings	Monthly
Recruitment of participants and informed consent	9 to 21
Randomization and baseline activities	22 to 25
Data cleaning, entry and analysis	9 to 52
Follow-up	26 to 45
Report writing and rounding up	45 to 52

Project management/logistics support

Staffing

For effective project implementation and management, the following staff would be required:

Role		% time	Responsibilities
Principal Investigator	1	25%	Oversees entire project, especially its scientific integrity

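### No instrument, visit or between-arm test is named as deciding whether SMS reminders work, and the proportion at least 95% adherent is compared with baseline rather than between arms

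*Combined protocol and SAP*

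**What the plan says.** All references are to the combined protocol and SAP.

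- **Expected Outcomes, Primary outcome measure:** "ART adherence will be assessed using the visual analog scale (VAS), Viral load, Pill count, Pharmacy record, and the AIDS Clinical Trials Group (ACTG" questionnaire. The section goes on to praise the VAS, but it does not say that the VAS, or any other measure, decides.
- **Statistical Methods, means:** an independent t-test of mean adherence between the arms is run "after each follow-up visit in order to test if the intervention has any effect". Follow-up gives five visits: weeks 4, 8, 12, 16 and 20.
- **Statistical Methods, proportion:** the proportion at least 95% adherent "at the end of the follow-up period will be compared with the baseline data using the chi-square test".
- **Statistical Methods, effect measures and analysis sets:** incidence proportion and rate are listed, and "relative risk, risk difference, and odds ratio will be used to measure the effect". Also, "Complete case analysis and the intention-to-treat analysis will be carried out". Neither list is ranked.
- **Study design and procedure:** 80% power for a difference of 20%, taking 49% as the proportion adherent and 10% attrition, gives 96 per group; 200 are to be recruited. Instrument, visit, significance level and sidedness are not given. Background reports 49%, under the same citation, as a viral suppression rate.
- **Participants' recruitment:** entry requires a VAS below 95%.
- **Intervention and Follow-up:** both arms receive adherence counselling at every visit and a clinic-based psychological intervention.
- **Data Analysis:** the data manager and investigators "will be responsible for baseline, interim and final data analysis". For the analysis, "unique identifiers in two groups will be sent to the data analysts without specifying which" group is which.

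**The concern.** Objective 1 asks whether SMS reminders improve adherence. The plan offers several ways to answer and no rule for choosing between them. There are two distinct problems.

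1. Five between-arm tests share the stated purpose of detecting an effect, on an outcome that five instruments could supply. Nothing prevents a difference at one visit from being reported as the result, and nothing says which measure prevails if self-report and viral load disagree.
2. The trial is sized for a difference in proportions, but the only test written out for a proportion is a before-and-after one. The between-arm comparison at week 20 exists only as one of five t-tests on means. The powered quantity therefore has no explicit randomised comparison.

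At stake is whether a positive report could be tied to a single pre-specified test with a known error rate.

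**Working it through.** **1. The plan's own figure.** Inputs from Study design and procedure: 49%, a 20-point difference (so 69%), 80% power, 1:1, 10% attrition. Assumed, because the plan is silent: two-sided 5%, pooled variance, no continuity correction.

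n = [1.96·√(2·0.59·0.41) + 0.8416·√(0.49·0.51 + 0.69·0.31)]² / 0.20² = (1.3633 + 0.5732)² / 0.04 = 93.7, so 94 evaluable per arm.

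With attrition: 94/0.9 = 104.4, so 105 enrolled per arm.

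Other conventions, before and after attrition:
- two-sided with continuity correction: 104, then 116;
- one-sided 5% with continuity correction: 84, then 94;
- one-sided 5% without it: 74, then 83.

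The stated 96 lies near 94 two-sided before attrition and near 94 one-sided after it. It equals none of these, and the plan does not say which was meant.

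Power with 200 enrolled and 10% lost (90 per arm), two-sided 5%: Φ[(0.20·√90 − 1.3633)/0.6810] = Φ(0.784) = 78.4%.

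**2. Five visits, one instrument.** Assumptions: no true effect, two-sided 5% per test, any significant visit read as success.

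If visits were independent: 1 − 0.95⁵ = 22.6% in either direction, and 1 − 0.975⁵ = 11.9% favouring SMS. Repeated measures on the same people are correlated, so this is an upper limit. Simulating five correlated normal test statistics (2,000,000 draws, |z| > 1.96) gives:

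| Between-visit correlation | Either direction | Favouring SMS |
|---|---|---|
| Equal, 0.5 | 18.2% | 9.1% |
| Equal, 0.8 | 12.7% | 6.4% |
| Equal, 0.9 | 10.2% | 5.1% |
| Decaying with visit gap, 0.5 | 20.2% | 10.2% |
| Decaying, 0.8 | 15.0% | 7.5% |
| Decaying, 0.9 | 11.9% | 5.9% |

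The nominal values are 5% and 2.5%. The documents give no correlations; these are a plausible span. For a false claim that SMS works, the last column is the relevant one.

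**3. The comparison with baseline.** No arithmetic is needed for the main point. Participants enter because their VAS is below 95%, and both arms then receive counselling at every visit and a psychological intervention. Counselling alone could raise the proportion at or above 95% in both arms, and a before-and-after test cannot separate that rise from an SMS effect.

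As an illustration of how little it takes, assume nobody in an arm is at 95% at baseline. Then 4 of 90 at week 20 gives an uncorrected chi-square of 180·(4·90)²/(90·90·4·176) = 4.09, p = 0.043. Adherence is measured again at baseline after screening, so a baseline of exactly zero is an assumption.

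**The case against.** **The VAS at 95% is evidently the primary measure.** It sets eligibility, it is the instrument the outcome section defends, and the 95% cut-off recurs in Statistical Methods. That makes it the best-supported choice, and it also weakens any count that multiplies all instruments by all visits. A reader might infer an error rate as high as 66% from 21 independent tests (four instruments at five visits plus viral load once), but mean percent adherence and a 95% cut-off do not describe a viral load, and the tests are not independent. Still, no section names the VAS as primary, and the 49% used for sizing appears in Background as viral suppression.

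**The t-tests are the efficacy analysis.** This stands in part: Statistical Methods gives them that purpose. It follows that a reader who infers that the baseline comparison is the efficacy test, or the only test at the end of follow-up, goes too far. Week 20 is one of the t-test visits, and the listed relative risk, risk difference and odds ratio are naturally read as between-arm measures. Any percentage for how often the baseline comparison would produce a false claim would need a decision rule and a baseline rate that the plan does not state. What remains is five tests with none decisive.

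**Analysts see unlabelled groups.** This limits choosing a result because it favours SMS. It does not stop choosing the visit or instrument where the groups differ.

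**A longitudinal analysis is planned.** Its stated role is exploratory: "Longitudinal data analysis will be carried out to explore the change in response over time".

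**The trial is too small.** A reader might infer this from 105 against 96. The documents do not support it, because the significance level, sidedness and endpoint are unstated.

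**Conclusion.** The concern holds. The plan has several tests of the intervention and none that decides. On one instrument, treating any significant visit as success raises the chance of a false finding to about 10–18% in either direction, or 5–9% in favour of SMS against a nominal 2.5%. This assumes two-sided 5% per test and equal between-visit correlation of 0.9 to 0.5; letting correlation decay with time raises it slightly.

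Separately, the proportion at least 95% adherent is written as a before-and-after comparison, which cannot isolate an SMS effect; that conclusion rests on the text alone. The figures of 94, 105 and 78% are conditional on 49% against 69% at two-sided 5% without continuity correction. They do not show that 96 is wrong.

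**What to change.** Make these changes before any outcome is compared by group, that is, before the two-group list goes to the analysts and before any interim analysis.

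1. Name one primary instrument at week 20. VAS at least 95% is best supported by the documents; the sponsor may choose another.
2. Replace the comparison with baseline by a between-arm comparison of that proportion at week 20, at a stated two-sided 5%, in the intention-to-treat set. Set the rule for missing week-20 values in advance and give complete-case as a sensitivity analysis. This test alone decides efficacy.
3. Report the other instruments, and weeks 4 to 16, as supportive estimates with confidence intervals.
4. State which endpoint, significance level and sidedness the sample size refers to, and justify the 49% for that endpoint or label it an assumption. If it is 49% against 69%, two-sided 5%, without continuity correction, restate it as 94 evaluable and 105 enrolled per arm, or about 78% power with 200 enrolled and 10% lost.

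**Cost.** No added data. An effect seen only at an earlier visit or on a supportive instrument could not be claimed as efficacy, and a dichotomised primary uses less information than the mean. The 78% is not a cost of the change: on those assumptions it is already the power of the present design. The missing-data rule does matter. Counting missing as non-adherent turns the rates into 0.49·0.9 = 44.1% and 0.69·0.9 = 62.1% on 100 per arm, with power about 73%.
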